6. GENERAL CONSIDERATIONS

The safety summaries, data listings and figures as well as the statistical analysis of the variables will be the responsibility of the study biostatistician at IQVIA.

6.1. SUMMARY STATISTICS

For qualitative variables, the population size (N for sample size and n for available data) and the percentage (of available data) for each class of the variable will be presented. Quantitative variables will be summarized using descriptive statistics, including N (with data available), mean, standard deviation (SD), median, Q1, Q3, minimum, and/or maximum values. Geometric mean will be included for immunogenicity parameters together with 95% confidence interval (CI), where applicable.

The exact two-sided 95% CIs for a proportion within a group will be calculated using the Clopper-Pearson exact method. The geometric mean antibody concentrations (GMCs) and titers (GMTs) calculations will be performed by taking the anti-log of the mean of the log10 titer transformations. Confidence interval for geometric means will be derived by raising 10 to the confidence interval associated with mean of log10 values i.e., CI of geometric mean = $10^{(CI \text{ for the mean of log10 values})}$. All participants with valid data will be considered. Participants whose antibody titers are below the cut-off of the assay will be given an arbitrary value of half the cut-off for the purpose of GMC/GMT calculation.

6.2. TREATMENT SUMMARIZATION

In general, data will be presented for each treatment group:

Country/Stage	Treatment
Europe/Stage 1	iNTS-TCV Low
	iNTS-GMMA + TCV Low
	Placebo
	iNTS-TCV Full
	iNTS-GMMA + TCV Full
Africa/Stage 2	iNTS-TCV Full
	iNTS-GMMA + TCV Full
	Control

Document: \\dccar2dnetvnasc01p-lan1.quintiles.net\cp_ops\PROJECTS\Glaxo SmithKline\GSK216152_WZA10802\SAP
Author: PPD Version Number: 2.0
Version Date: 07DEC2023

Template No: CS_TP_BS016 – Revision 7
Effective Date: 01Nov2021

Reference: CS_WI_BS005

Data for All Stage 1, All Stage 2 and All Study Participants combined will also be presented when appropriate.

6.3. PRECISION

Safety data (vital signs, laboratory parameters) and immunogenicity data will be reported to the same precision as the source data.

For the reporting of descriptive statistics, the mean, median, Q1, Q3, standard deviation, standard error and confidence intervals will be presented to one digit more precision than the source data. The minimum and maximum will be presented to the same precision as the source data. P-values, if any, shall be reported to four decimal places or as <0.0001.

Geometric mean concentrations (GMC)/titers (GMT), geometric mean ratios (GMR) and their confidence limits will always be shown with 2 decimal places.

6.4. REFERENCE START DATE AND STUDY DAY

Study Day will be calculated from the reference start date and will be used to show start/stop day of assessments and events.

Reference start date is defined as the day of the first dose of study vaccination, (Day 1 is the day of the first dose of study treatment) and will appear in every listing where an assessment date or event date appears.

- If the date of the event is on or after the reference date, then:

Study Day = (date of event – reference date) + 1.

- If the date of the event is prior to the reference date, then:

Study Day = (date of event – reference date).

In the situation where the event date is partial or missing, Study Day, and any corresponding durations will appear partial or missing in the listings. Refer to Section 7.1.1 for rules applicable on partially completed dates when used in calculations.

6.4.1. ATTRIBUTING EVENTS TO VACCINE DOSES

The dose relative to an event is the most recent study dose given to a participant prior to the start of a given event. For example, if the start date of an adverse event is between Dose 1 and Dose 2, the relative dose will be Dose 1.

If an event starts on the same day as a study dose, the relative dose will be derived from the additional information provided in the CRF using the contents of the flag indicating if the event occurred before

Document:	\dccar2dnetvnasc01p-lan1.quintiles.net\cp_ops\PROJECTS\Glaxo SmithKline\GSK216152_WZA10802\SAP		
Author:	PPD	Version Number:	2.0
		Version Date:	07DEC2023

Template No: CS_TP_BS016 – Revision 7
Effective Date: 01Nov2021

Reference: CS_WI_BS005

or after vaccination. If 'after vaccination' is selected or if the selection is missing, the relative dose for the event will be the one administered on the start day of the event. If 'before vaccination' is selected, the relative dose for the event will be the dose prior to this one. Where applicable, the event will be classified as "pre-treatment".

6.5. BASELINE

Baseline is defined as the last scheduled measurement taken prior to vaccination and will correspond to:

- Day 1 pre-dose for seroresponse calculation (4-fold for Anti-serotype specific IgG and \geq CCI for Anti-S. Typhi Vi Ag IgG antibody concentrations and GMR)
- Each vaccination pre-dose for immunogenicity within-participant GMR assessments, hematology, biochemistry and vital signs.

If a participant is missing the planned individual vaccination pre-dose result, change from baseline will not be calculated for within-participant GMR, hematology and biochemistry.

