
Endpoint	Statistical Analysis Methods
	
 - The maximum Grade from Day 1 until the end of the participant's participation will be tabulated. 
The verbatim reports of unsolicited symptoms will be reviewed by a physician and the signs and symptoms will be coded according to the MedDRA Dictionary for AE Terminology.

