Appendix 7 Grading Scales for Hematology and Biochemistry Safety Laboratory Assessments

The details of grading scales are provided in [Table 19](#) and [Table 20](#).

Table 19 Stage 1 – Adults (Europe)

Laboratory test	Mild (Grade 1)	Moderate (Grade 2)	Severe (Grade 3)	Potentially life--threatening (Grade 4)
Creatinine – mg/dL (male)	>1.17 – 1.7	>1.7 – 2.0	>2.0 – 2.5	>2.5 or requires dialysis
Creatinine – mg/dL (female)	>0.96 – 1.7	>1.7 – 2.0	>2.0 – 2.5	>2.5 or requires dialysis
Liver Function Tests –ALT, AST increase by factor	$\geq 1.1 - 2.5 \times$ ULN	$>2.5 - 5.0 \times$ ULN	$>5.0 - 10 \times$ ULN	$>10 \times$ ULN
Hemoglobin (female) - g/dL	11.0 – <11.8	9.5 – <11.0	8.0 – <9.5	<8.0
Hemoglobin (female/male) change from baseline value - g/dL	Any decrease – 1.5	>1.5 – 2.0	>2.0 – 5.0	>5.0
Hemoglobin (male) - g/dL	12.5 – <12.9	10.5 – <12.5	8.5 – <10.5	<8.5
WBC Increase - cell/mm ³	>9300 – 15000	>15000 – 20000	>20000 – 25000	>25000
WBC Decrease - cell/mm ³	2500 – <3650	1500 – <2500	1000 – <1500	<1000
Platelets Decreased - cell/mm ³ (male)	125000 – <149000	100000 – <125000	25000 – <100000	<25000
Platelets Decreased - cell/mm ³ (female)	125000 – <171000	100000 – <125000	25000 – <100000	<25000
Neutrophils Decrease - cell/mm ³	1500 – <1573	1000 – <1500	500 – <1000	<500
Lymphocytes decrease cell/mm ³	750 - <1133	500 - <750	250 - <500	<250
Eosinophils Cell/mm ³	>273 - 1500	>1500 - 5000	>5000	Hypereosinophilic

Abbreviations: ALT=alanine aminotransferase; AST = aspartate aminotransferase; ULN=upper limit of normal; WBC=white blood cell

The grading scale has been adapted from the Food and Drug Administration (FDA) Guidance for Industry- Toxicity Grading Scale for Healthy Adult and Adolescent Volunteers Enrolled in Preventive Vaccine Clinical Trials [[US Department of Health and Human Services](#), 2007] and adjusted considering local reference ranges provided by the site. Parameters not included in the FDA grading scales will not be graded; their assessment will be based on laboratory reference ranges and medical judgment.

Table 20 Stage 2 – Adults (Africa)

Laboratory test	Mild (Grade 1)	Moderate (Grade 2)	Severe (Grade 3)	Potentially life- threatening (Grade 4)

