Creatinine	$\geq 1.1 - 1.3 \times \text{ULN}$	$>1.3 - 1.8 \times \text{ULN}$ OR Increase to 1.3 to $<1.5 \times$ participant's baseline	$>1.8 - <3.5 \times \text{ULN}$ OR Increase to 1.5 to $<2.0 \times$ participant's baseline	$\geq 3.5 \times \text{ULN}$ OR Increase of $\geq 2.0 \times$ participant's baseline
Liver Function Tests –ALT, AST	$\geq 1.25 - <2.5 \times \text{ULN}$	$2.5 - <5.0 \times \text{ULN}$	$5.0 - <10.0 \times \text{ULN}$	$\geq 10.0 \times \text{ULN}$
Hemoglobin (female) - g/dL	$9.5 - <11.4$	$8.5 - <9.5$	$6.5 - <8.5$	<6.5
Hemoglobin (male) - g/dL	$10.0 - <11.4$	$9.0 - <10.0$	$7.0 - <9.0$	<7.0
WBC Decrease - cell/mm ³ (male/female)	$2000 - <2400$	$1500 - <2000$	$1000 - <1500$	<1000
Platelets Decreased - cell/mm ³ (male/female)	$100000 - <117000$	$50000 - <100000$	$25000 - <50000$	<25000
Neutrophils Decrease - cell/mm ³ (male/female)	$700 - <750$	$600 - <700$	$400 - <600$	<400
Lymphocytes decrease cell/mm ³ (male/female)	$600 - <830$	$500 - <600$	$350 - <500$	<350

Abbreviations: ALT=alanine aminotransferase; AST=aspartate aminotransferase; ULN=upper limit of normal; WBC=white blood cell. The grading scale has been adapted from the Division of AIDS (DAIDS) Table for Grading the Severity of Adult and Pediatric Adverse Events [[US Department of Health and Human Services](#), 2017] and adjusted considering local normal ranges provided by the site. Parameters not included in the DAIDS grading scales will not be graded and their assessment will be based on laboratory normal ranges and medical judgment.

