3.3. CHANGES TO ANALYSIS FROM PROTOCOL

Entered Set is defined in Section 5 to comprise of participants who provide informed consent for the

Document: \\dccar2dnetvnasc01p-lan1.quintiles.net\cp_ops\PROJECTS\Glaxo SmithKline\GSK216152_WZA10802\SAP
 Author: PPD Version Number: 2.0
 Version Date: 07DEC2023

Template No: CS_TP_BS016 – Revision 7
 Effective Date: 01Nov2021

Reference: CS_WI_BS005

study.

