6.6. COMMON CALCULATIONS

For quantitative safety measurements (e.g., vital signs, laboratory parameters), change from baseline will be calculated as:

- Observed Value (after baseline) – Baseline Value (exceptions might apply as per protocol grading scale table, e.g., creatinine in Stage 2).

For immunogenicity measurements, change from baseline will be calculated as:

- Test Value (after baseline)/Baseline Value.

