16.2. SAFETY LABORATORY EVALUATIONS

Laboratory results will be included in the reporting of this study for Hematology and Biochemistry. A list of laboratory assessments to be included in the outputs is included in Table 9 of the protocol.

For each group and for each haematology and biochemistry parameter:

- The percentage of participants having hematology and biochemistry results below/within/ above the local laboratory ranges versus baseline will be tabulated by treatment, timepoint and stage.
- The percentage of participants with hematology and biochemistry results by grade versus baseline will be tabulated by treatment, timepoint and stage.

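### With laboratory baseline reset before each dose, unrecovered change grades lower than from Day 1 in two baseline-relative rows; separately, the maximum-grade table is absent from the SAP text

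*SAP*

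**What the plan says.** SAP 6.5 defines baseline as the last scheduled measurement before vaccination. It uses the Day 1 value for seroresponse, but for laboratory data it uses "Each vaccination pre-dose for immunogenicity within-participant GMR assessments, hematology, biochemistry and vital signs". If that pre-dose sample is missing, "change from baseline will not be calculated for within-participant GMR, hematology and biochemistry", and there is no fallback to Day 1. SAP 6.6 defines laboratory change as observed minus baseline and adds that "exceptions might apply as per protocol grading scale table, e.g., creatinine in Stage 2".

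Protocol Appendix 7 has two graded rows that refer to the participant's own baseline. In Stage 1 (Table 19) the row is "Hemoglobin (female/male) change from baseline value - g/dL". In Stage 2 (Table 20) creatinine is graded partly as a multiple of the participant's baseline. All other graded rows use absolute values or multiples of ULN.

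On summaries, protocol 9.4.1 (Table 11) states: "The maximum Grade from Day 1 until the end of the participant's participation will be tabulated". SAP 16.2 plans two tabulations. One classifies results as below, within or above the local range versus baseline. The other reads: "The percentage of participants with hematology and biochemistry results by grade versus baseline will be tabulated by treatment, timepoint and stage". SAP 3.3 lists only the new Entered Set as a change from the protocol.

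**The concern.** The laboratory part of the primary endpoint is deviation from normal or baseline values over a three-dose course, in a vaccine given to humans for the first time. If a haemoglobin fall or a creatinine rise after one dose persists to the next pre-dose sample, the SAP makes the shifted value the new reference. A stepwise change is then split into per-dose pieces, each of which may fall in a low grade or in none. The information matters most for repeated dosing, where the question is whether change accumulates.

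The maximum-grade table is a separate matter. Tables by time point do not show how many participants had a given worst grade during the study, because the same participant can appear at several time points.

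**Working it through.** The plan contains no figure that depends on the laboratory baseline, so there is nothing to reproduce. The check applies the protocol's own cut-offs with each baseline.

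**Inputs (protocol Tables 19 and 20)**
- Stage 1 haemoglobin fall: any to 1.5 g/dL = Grade 1; >1.5 to 2.0 = Grade 2; >2.0 to 5.0 = Grade 3; >5.0 = Grade 4.
- Stage 1 absolute haemoglobin: grading starts below 11.8 g/dL (female) or 12.9 g/dL (male).
- Stage 2 creatinine ratio to baseline: 1.3 to <1.5 = Grade 2; 1.5 to <2.0 = Grade 3; ≥2.0 = Grade 4. The ULN-based scale starts at 1.1 × ULN.
- The starting values and per-dose changes below are illustrative assumptions.

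**Haemoglobin, woman, 15.0 → 13.6 → 12.2 g/dL over two doses**
- Per dose: 15.0 − 13.6 = 1.4 and 13.6 − 12.2 = 1.4; Grade 1 each time.
- From Day 1: 15.0 − 12.2 = 2.8; Grade 3.
- Absolute: 12.2 is above 11.8; no grade.

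**Haemoglobin, man, 16.0 g/dL, losing 1.0 per dose over three doses**
- Per dose: Grades 1, 1, 1.
- From Day 1: falls of 1.0, 2.0 and 3.0; Grades 1, 2, 3.
- Absolute: 13.0 is above 12.9; no grade.

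More generally, a fully carried-over fall of 0.7 to 1.5 g/dL per dose is Grade 1 each time but totals 2.1 to 4.5 g/dL, which is Grade 3 from Day 1 after dose 3.

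**Creatinine, 0.60 → 0.75 → 0.93 mg/dL over two doses**
- Per dose: 0.75/0.60 = 1.25 and 0.93/0.75 = 1.24; both below 1.3, so ungraded.
- From Day 1: 0.93/0.60 = 1.55; Grade 3.
- This assumes that 0.93 is below 1.1 × ULN, that is, ULN above 0.93/1.1 ≈ 0.85 mg/dL. The documents give no Stage 2 ULN.
- Over three doses, a constant ratio of 1.15 gives 1.15³ = 1.52 (Grade 3), and 1.29 gives 2.15 (Grade 4); each is ungraded per dose.

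**How far the absolute scale compensates (Stage 1 haemoglobin, three doses)**
- Man from 14.5, losing 1.0 per dose: 11.5, absolute Grade 2.
- Woman from 13.0, losing 1.2 per dose: 9.4, absolute Grade 3.

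The absolute scale therefore compensates for participants who start low and not for those who start high.

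**Probability of change Grade ≥3 after dose 3 (simulation)**
This assumes a carried-over fall c per dose and independent within-person variation with SD s on each sample. The fall exceeds 2.0 g/dL with probability 1 − Φ((2.0 − d)/(s√2)), where d = c for the per-dose baseline and d = 3c for Day 1. The values of s are assumptions.

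| c (g/dL) | s = 0.3, per-dose | s = 0.3, Day 1 | s = 0.5, per-dose | s = 0.5, Day 1 |
|---|---|---|---|---|
| 0 | 0.0% | 0.0% | 0.2% | 0.2% |
| 0.4 | 0.0% | 3.0% | 1.2% | 12.9% |
| 0.7 | 0.1% | 59.3% | 3.3% | 55.5% |
| 1.0 | 0.9% | 99.1% | 7.9% | 92.2% |

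If values recover fully before the next dose, d is the same for both baselines and so are the rates. If a pre-dose value lies above the Day 1 value, the per-dose baseline gives the higher grade.

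**Shift tables**
Take a participant who is normal on Day 1, Grade 1 at Day 57 and Grade 2 after dose 2, on any parameter. The table shows normal to Grade 1 after dose 1 and Grade 1 to Grade 2 after dose 2. The shift from normal to Grade 2 appears nowhere, although each grade is correct.

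**Maximum grade**
For the woman above, the maximum over per-dose grades is 1 and the maximum over Day 1-based grades is 3. Adding the table without stating its baseline would leave the first problem in place.

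**The case against.** The strongest reply is that a per-dose reference fits the endpoint, which assesses laboratory values 7 and 28 days after each administration. The protocol never defines laboratory baseline as Day 1, although for immunogenicity it does distinguish the first-dose baseline from each dose's own. This stands: the reset resolves an ambiguity and does not contradict a protocol rule. The exception in SAP 6.6 loosens the creatinine case only slightly, because it concerns the formula and not which sample is the reference.

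A reader might infer that cumulative decline is under-graded across the laboratory panel. The documents do not support that. White cells, platelets, neutrophils, lymphocytes, ALT/AST, absolute haemoglobin and Stage 1 creatinine keep their grade whatever the baseline. Of the two affected rows, creatinine is a rise, and Stage 2 (105 of 155 participants) has no baseline-relative row for a decline. A reader might also infer that the missing table causes the lower grades; a summary table cannot alter a grade.

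Nor do the documents show that safety oversight would miss such a change. The iSRC reviews all available safety data cumulatively (protocol 9.7), investigators review each laboratory report (8.3.2.1), the latest results are used to assess eligibility for doses 2 and 3 (5.5), and the iSRC/SRT analyses are described in a separate document (SAP 1).

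Finally, the table shells are separate (SAP 8) and were not available, so the maximum-grade table may be there. That limits the point to the SAP text.

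**Conclusion.** The concern holds in a limited form. The reset is explicit. In two graded rows it can lower the grade of an unrecovered change: by two grades in the haemoglobin examples, and from Grade 3 to ungraded in the creatinine example. After doses 2 and 3 it also removes the shift from the pre-vaccination state for all parameters.

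The grading effect rests on non-recovery to the next pre-dose sample, planned 56 days after dose 1 and 112 days after dose 2. The documents give no reason to expect that, but the analysis should be able to show it. Its size also depends on the assumed starting values, per-dose changes, within-person SD of 0.3 to 0.5 g/dL and Stage 2 ULN.

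The omission of the maximum-grade summary from the SAP text, undeclared in SAP 3.3, needs none of these assumptions. Neither point changes a sample size or a test. Both bear on how completely a primary safety endpoint is reported, and both are worth correcting before the tables are produced.

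**What to change.** 1. Keep the per-dose change as planned.
2. In SAP 6.5, name the reference for the two baseline-relative rows and add a Day 1 pre-vaccination baseline for haematology and biochemistry. SAP 15 already tabulates within-participant GMR against both each pre-dose value and Day 1, so this follows the plan's own practice. It also gives a result when a later pre-dose sample is missing.
3. In SAP 16.2, add Day 1-based change and shift tables for all haematology and biochemistry parameters, and Day 1-based grades for the two affected rows.
4. Put the maximum-grade table from protocol Table 11 into SAP 16.2, state which baseline its baseline-relative grades use, and show the Day 1-based version. A composite of the worst grade over several definitions is not needed and appears in neither document. If the sponsor means to drop the table, declare that in SAP 3.3.

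The cost is one extra set of tables from samples already scheduled (Days 1, 8, 29, 57, 64, 85, 169, 176 and 197), and possibly higher reported grades for a few participants.

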6.6. COMMON CALCULATIONS

For quantitative safety measurements (e.g., vital signs, laboratory parameters), change from baseline will be calculated as:

- Observed Value (after baseline) – Baseline Value (exceptions might apply as per protocol grading scale table, e.g., creatinine in Stage 2).

For immunogenicity measurements, change from baseline will be calculated as:

- Test Value (after baseline)/Baseline Value.

6.7. SOFTWARE VERSIONS

All derivations, statistical analyses, summaries, graphs and listings will be generated using SAS version 9.4 or higher (SAS Institute, Inc., Cary, North Carolina).

7. STATISTICAL CONSIDERATIONS

7.1. MISSING DATA

Missing immunogenicity data will be handled as described in Section 15. Following imputation will be

Document:	\dccar2dnetvnasc01p-lan1.quintiles.net\cp_ops\PROJECTS\Glaxo SmithKline\GSK216152_WZA10802\SAP		
Author:	PPD	Version Number:	2.0

Template No: CS_TP_BS016 – Revision 7
Effective Date: 01Nov2021

Reference: CS_WI_BS005

used for statistical calculations (and not for participant listings):

7.1.1. DATES

When partially completed dates (i.e., with missing day or month) are used in calculations, the following standard rules will be applied:

- A missing day will be replaced by 15
- A missing day and month will be replaced by June 30th

The following exceptions apply:

- Adverse event start dates with missing day:
 - o If the event starts in the same month as at least one of the study doses, the contents of AE.AESTRTPT (the flag indicating if the event occurred before or after vaccination) will be used to complete the date. If 'after vaccination' is selected or if the selection is missing, the imputed start date will match the first (or only) study dose given during that month. If 'before vaccination' is selected, the imputed date will be one day before the first (or only) study dose given during that month.
- Adverse event start dates with missing day and month:
 - o If the event starts in the same year as at least one of the study doses, the contents of AE.AESTRTPT (the flag indicating if the event occurred before or after vaccination) will be used to complete the date. If 'after vaccination' is selected, the imputed start date will match the first (or only) study dose given during that year. If 'before vaccination' is selected, the imputed date will be one day before the first (or only) study dose given during that year.

All other cases of incomplete AE or concomitant medication/vaccination start date will follow the standard rules as outlined in Section 6.4.

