
 • The term disability means a substantial disruption of a person's ability to conduct normal life functions. • This definition is not intended to include experiences of relatively minor medical significance such as uncomplicated headache, nausea, vomiting, diarrhea, influenza, and accidental trauma (eg, sprained ankle) which may interfere with or prevent everyday life functions but do not constitute a substantial disruption.
e) Abnormal pregnancy outcomes (eg, spontaneous abortion, fetal death, stillbirth, congenital anomalies, ectopic pregnancy)

f) Other situations:

- Medical or scientific judgment should be exercised in deciding whether SAE reporting is appropriate in other situations such as important medical events that may not be immediately life-threatening or result in death or hospitalization but may jeopardize the participant or may require medical or surgical intervention to prevent 1 of the other outcomes listed in the above definition. These events should usually be considered serious.

Examples of such events include invasive or malignant cancers, intensive treatment in an emergency room or at home for allergic bronchospasm, blood dyscrasias or convulsions that do not result in hospitalization, or development of drug dependency or drug abuse.

Solicited Events

Events to be recorded as endpoints in the clinical study. The presence/occurrence/intensity of these events is actively solicited from the participant or an observer during a specified follow-up period following study intervention administration.

Table 17 Solicited Events to be Collected

Solicited administration site events	Pain at administration site
	Redness at administration site
	Swelling at administration site
Solicited systemic events	Fever
	Headache
	Myalgia
	Arthralgia
	Fatigue

Participants will be instructed to measure and record the axilla temperature in the evening. If additional temperature measurements are taken at other times of the day, participants will be instructed to record the highest temperature in the pDiary card.

Unsolicited Events

Any AE reported in addition to those solicited during the clinical study. Also, any 'solicited' symptom with onset outside the specified period of follow-up for solicited symptoms will be reported as unsolicited AEs. Unsolicited events will be collected for 28 days after each study intervention administration (ie, Day 1 to Day 28, Day 57 to Day 84 and Day 169 to Day 196).

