The analysis of unsolicited adverse event will be performed in the Unsolicited Safety Set. The verbatim reports of unsolicited symptoms will be reviewed by a physician and the signs and symptoms will be coded per the Medical Dictionary for Regulatory Activities (MedDRA), Version 26.0 or higher. Every verbatim term will be matched with the appropriate preferred term (PT). The percentage of participants with unsolicited AEs within 28 days after any doses with its exact 95% CI will be tabulated by group, stage and by MedDRA preferred term. Similar tabulation will be done for Grade 3 unsolicited AEs, for unsolicited AEs that resulted in a medically attended visit, for Grade 3 and causally related unsolicited AEs and for unsolicited AEs causally related to vaccination. These tabulations will include System Organ Class (SOC) and SOC/PT analyses.

The number of participants who experienced at least 1 SAE within 28 days after any dose, from dose 1 until 28 days post last dose (Day 197) and from Day 198 until Day 337 will be reported by treatment.

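### Outside the dose-month and dose-year exceptions, SAP 7.1.1 imputes a missing AE start day as the 15th with no bound at the 28-day window, and end dates with no bound at the event's start

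*SAP*

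**What the plan says.** SAP 7.1.1 sets two defaults for partial dates used in calculations: "A missing day will be replaced by 15" and "A missing day and month will be replaced by June 30th".

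Two exceptions follow, both for AE start dates only.

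- **Day missing, month contains a dose.** "If 'after vaccination' is selected or if the selection is missing, the imputed start date will match the first (or only) study dose given" in that month. If the flag says before vaccination, the date is one day before that dose.
- **Day and month missing, year contains a dose.** The same approach with the first dose of that year, but the wording covers only a flag of after or before. A blank flag is not mentioned.

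The section closes: "All other cases of incomplete AE or concomitant medication/vaccination start date will follow the standard rules as outlined in Section 6.4". SAP 6.4 sends the reader back: "Refer to Section 7.1.1 for rules applicable on partially completed dates when used in calculations".

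The dates are used in these places:

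- Protocol Appendix 3 (Unsolicited Events): "Unsolicited events will be collected for 28 days after each study intervention administration". Protocol Table 3 defines the window as the dose day and the 27 days after it, and makes this a primary endpoint.
- SAP 16.1 tabulates it: "The percentage of participants with unsolicited AEs within 28 days after any doses".
- SAP 7.2.4 computes duration as end minus start plus one day.
- SAP 13 calls a medication prior if it started and stopped before the first dose.

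**The concern.** Unsolicited AEs are collected for 28 days after each dose, so an AE recorded in the month after a dose would usually have started early in that month, before the window closed. The default ignores this and puts it on the 15th, which for many dose dates lies beyond day 28. The event then leaves the table that reports a primary safety endpoint. Whether it stays depends on the calendar day of the dose.

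The two rules also pull in opposite directions. In a dose month an AE not flagged as before vaccination goes to the dose date and is kept, which is conservative for safety. In the next month the default can only lose an in-window event, which is anti-conservative. Groups are small (4, 16, 45 and 15 participants on vaccine or Stage 2 control), so one participant whose only AE is dropped moves a percentage by 1/45 = 2.2 points up to 1/4 = 25 points.

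Partial end dates have no exception at all. An imputed end can fall before the start, and an imputed medication stop date can fall before dose 1 when the medication in fact continued past it.

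**Working it through.** **Plan's own figure.** SAP 7.2.4 gives 03MAR2018 to 12MAR2018 as 10 days: 12 − 3 + 1 = 10. It reproduces. The documents give no figure for the effect of date imputation.

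**Start date, one case.** Dose 10 June. The window ends on 10 June + 27 days = 7 July. An AE dated only as July, if in the window, began on 1-7 July. July contains no dose, so the default gives 15 July. Onset day = 15 July − 10 June + 1 = 36, which exceeds 28, so the AE leaves the table.

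**Which dose days are affected.** In a 31-day month, doses on days 1-4 have windows that end within the month. For doses on days 5-18 the window reaches the next month, but the 15th of that month is onset day 42 down to 29, so it is outside. For doses on days 19-31 the 15th is onset day 28 down to 16, so it is inside. That is 14 affected dose days. Shorter months also have 14, shifted earlier.

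**Share affected.** Assumptions: only the start day is missing; the flag is after or blank; true onset is uniform over days 1-28; dose dates are spread evenly over 2023; the next month contains no dose.

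| Quantity | Count | Share |
|---|---|---|
| Dose date × onset day combinations | 365 × 28 = 10,220 | |
| Onset in the month after the dose | 12 × (1 + … + 27) = 12 × 378 = 4,536 | 4,536/10,220 = 44.4% |
| Of these, imputed outside the window | 12 × (1 + … + 14) = 12 × 105 = 1,260 | 1,260/4,536 = 27.8% |
| Imputed outside, of all in-window onsets | 1,260 | 1,260/10,220 = 12.3% |
| Dose dates affected | 12 × 14 = 168 | 168/365 = 46.0% |

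The other 55.6% of onsets fall in the dose month and go to the dose date. With all three doses at the planned 56- and 112-day intervals, or at the extremes of the allowed ranges, the share imputed out stays at 12.3%.

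**Where the losses sit.** No true onset on days 1-14 is lost. All 1,260 losses have true onset on days 15-28, and 57% of them on days 24-28.

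**End date.** Start 20 May, end dated only as May: the default gives 15 May, and the duration is 15 − 20 + 1 = −4 days. If the end is in the same month as the start, the imputed end precedes every start on day 16 or later: 185 of 365 start dates, 51%. Allowing the end to run into the next month, the share is 51% for a true duration of 1 day and falls to 31% for 7 days. The dose-month exception can itself cause this: dose on the 20th, start set to the 20th, end set to the 15th.

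**Medication.** Dose 1 on 20 May, medication started in April and stopped on 25 May, with the stop recorded only as May. The imputed stop is 15 May, before dose 1, so SAP 13 classes it as prior.

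**Year-only AE start with a blank flag.** The exception does not cover it, so June 30 applies. If dose 1 was in July or later of that year, the imputed start precedes all dosing.

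**Fix checked.** With the first of the month used for a start in a month without a dose, the same enumeration loses 0 of the 4,536 next-month onsets.

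**The case against.** The strongest reply is that little is likely to change. Visits fall 7-10 and 28-33 days after each dose (Protocol Table 2), and Protocol Appendix 3 has unsolicited AEs collected by interview and record review at the next visit, so dates missing the day should be uncommon. The 12% is conditional on a missing day and on uniform onset. Since only onsets on days 15-28 can be lost, the share falls towards zero if AEs cluster early. All of this stands and limits the size of the point.

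A reader might infer stronger things that the documents do not support:

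- **That every missing day becomes the 15th.** It does not. The dose-month exception takes more than half of in-window onsets and keeps them in the window when the flag is after or blank.
- **That impossible durations will be reported.** SAP 7.1 restricts imputation to calculations, and under SAP 6.4 "any corresponding durations will appear partial or missing in the listings". SAP 16.1 names no table of unsolicited-AE duration, and solicited duration is taken from the first and last symptom dates.
- **That the reference to 6.4 leaves the rule undefined.** The pointer is circular, but it returns the programmer to 7.1.1. It is an editorial slip.
- **That a year-only date with a blank flag has no rule.** The closing sentence sends it to the default. The case needs three items missing at once.

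The first-of-month convention has its own bias: an event that truly began after day 28 can be moved in. That is a fair cost, and it errs towards keeping safety events.

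**Conclusion.** The rule as written is wrong for one defined set of dates: AE start dates with a missing day, in a month without a dose, where the true onset was inside the 28-day window. For these the SAP can remove an event from a primary safety table. The size is about 12% of in-window AEs with a missing start day, assuming uniform onset over days 1-28 and dose dates spread evenly over the year, with every loss at true onset on days 15-28. The number of such dates is not documented and is probably small, so no change in a reported percentage can be claimed.

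The end-date gap is real but has no shown effect on a named AE table. Its one route to an output in the SAP text is prior versus concomitant status and the 28-day concomitant-medication summary. The blank-flag omission is a rare case. This is a low-severity point, worth correcting because the correction is cheap and conservative for safety.

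**What to change.** Amend SAP 7.1.1 as follows.

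1. Where the month is known and contains no dose, impute a missing AE start day as the first day of that month. Keep the existing dose-month rule.
2. In the missing-day-and-month exception, treat a blank before/after flag as after vaccination, as the missing-day exception already does. Keep the rule that the first dose of that year applies.
3. Impute a missing AE or medication end day as the last day of the known month, capped at last contact and never before the start date.
4. Editorial: change the closing reference from Section 6.4 to Section 7.1.1.

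The cost is a few lines of SAP text and code. The downside is that a few AEs of uncertain date stay in the 28-day table and some imputed durations are slightly long.
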